### 7.3 Statistical Analysis of Pharmacokinetic Parameters

As an exploratory analysis, PK parameters for observed and BL-adjusted serum calcifediol will be compared between treatments using a mixed-effects model for the PK population. The dependent variable will be the value of the PK parameter. The model will include a term for treatment and BL calcifediol as a covariate. The PK parameters

compared may include  $C_{max}$  and  $AUC_{0-24h}$  for Day 1 and  $C_{max}$ ,  $AUC_{0-24h}$  (ie,  $AUC_{tau}$  for daily dosing regimen), and  $C_{avg}$  for Day 29. Additional parameters (eg, alternative  $AUC_{0-t}$  parameters) may be compared (and/or substituted) as deemed appropriate.

[figure not shown]
Treatment least-squares means and least-squares differences and 95% confidence intervals for the difference will be constructed for the values of each parameter. In addition, the  $P$  values will be presented for treatment and BL in the analysis table.

The SAS Proc Mixed code is as follows:

[figure not shown]
```
PROC MIXED DATA = adpc;
  BY paramn paramcd param;
  CLASS trtp;
  MODEL aval = trtp base_calcifediol;
  ESTIMATE 'CTAP101 Capsules vs. Calcifediol IR' trtp 1 -1 0 0 / cl;
  ESTIMATE 'CTAP101 Capsules vs. Cholecalciferol' trtp 1 0 -1 0 / cl;
  ESTIMATE 'CTAP101 Capsules vs. Paracalcitol plus cholecalciferol' trtp 1 0 0 -1 / cl;
  RUN;
```

[figure not shown]
Alternative statistical analyses may be provided if insufficient data or issues with the model are found.

CCI

CCI

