An Open-Label, Repeated-Dose Safety, Efficacy, Pharmacokinetic and Pharmacodynamic Study of Oral CTAP101 Capsules, IR Calcifediol, High-Dose Cholecalciferol, and Paricalcitol Plus Low-Dose Cholecalciferol in Patients with Secondary Hyperparathyroidism, Stage 3 or 4 Chronic Kidney Disease and Vitamin D Insufficiency.

Study Number:

CTAP101-CL-4001

Study Phase: 4

Objectives:

The objectives of this study are to assess the repeated-dose safety, efficacy, pharmacokinetic (PK) **CCI** profiles of CTAP101 Capsules, IR calcifediol, high-dose cholecalciferol, and paricalcitol plus low-dose cholecalciferol in patients with secondary hyperparathyroidism (SHPT), stage 3 or 4 chronic kidney disease (CKD) and vitamin D insufficiency (VDI).

[figure not shown]
Study Design:

This is a phase 4, multi-center, 4-arm, open-label study to gather comparative data evaluating the safety, efficacy and PK **CCI** profiles for CTAP101 Capsules, IR calcifediol, high-dose cholecalciferol, and paricalcitol plus low-dose cholecalciferol to treat SHPT in male and female subjects aged at least 18 years with stage 3 or 4 CKD and VDI. The study will be conducted at multiple sites within the United States (US). Approximately 160 subjects will be screened to

enroll approximately 80 eligible subjects who will be randomized 1:1:1:1 (approximately 20 per arm, balanced for body weight) to receive 8 weeks of treatment as follows: CTAP101 Capsules at a dose of 60 mcg per day; IR calcifediol at a dose of 266 mcg on Day 1 and Day 29; high-dose cholecalciferol at a dose of 300,000 IU on Day 1 and Day 29; and paricalcitol at a dose of 1 mcg per day (possibly increasing to 2 mcg per day at Day 29) plus low-dose cholecalciferol 800 IU per day. If a significant difference in average weight among subjects by treatment group emerges during the course of the study, subjects may be placed into specific treatment groups rather than randomly assigned, in order to try and achieve more balance in the treatment groups by body weight.

The subjects will be housed in a phase 1 unit for approximately 14 to 26 hours at the beginning of the study and on study Day 29 to provide the blood samples required for a detailed determination of the PK profiles for serum calcifediol (25D₃) **CCI**

CCI

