5.4 Method of Assigning Subjects to Treatment Groups

After signing the ICF, prior to any study-related activities, each subject will be assigned a unique 7 digit subject identification number which will be retained throughout the study and that will be unique across all sites. The 7 digit subject identification number (SSSNNNN) will consist of a 3-digit site number (SSS) and a 4-digit subject number (NNNN) at the applicable clinical site. Should a subject be withdrawn from the study, that subject's 7 digit identification number will not be reassigned.

Randomization will be accomplished in blocks of 4 subjects in a 1:1:1:1 ratio with subjects being assigned to treatment with CTAP101 Capsules, IR calcifediol, high-dose cholecalciferol or paricalcitol plus low-dose cholecalciferol. Randomization will occur during Visit 4 provided that each subject is deemed eligible for enrollment based, in part, on laboratory assessments obtained at the preceding visit (Visit 1). Laboratory assessments obtained at Visits 2-3 will not be considered in the determination of enrollment eligibility.

In the event that a significant difference in mean baseline body weight among subjects by treatment group emerges as enrollment progresses, the randomization scheme (described immediately above) will be suspended and subjects will be assigned to a specific treatment group using the following alternative procedure:

Step 1: Calculate the mean body weight for subjects who have been previously entered into the treatment period, in aggregate and by treatment group.

Step 2: Compare the subject's body weight (measured at Visit 1) with the current mean body weight of all subjects who have previously been entered into the treatment period. If the subject's weight is equal to or higher than the current mean body weight of all previously treated subjects, then assign the subject to a treatment group (which still has less than 20 subjects) having the lowest mean body weight. If the subject's weight is lower than the current mean body weight of all previously treated subjects, then assign the subject to a treatment group (which still has less than 20 subjects) having the highest mean body weight.

Step 3 (if needed): If a subject cannot be assigned to a treatment group according to Step 2 (above) and there are fewer than 80 subjects assigned to treatment, then assign the subject to a treatment group (which still has less than 20 subjects) with the most similar mean body weight.

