9.3 Randomization

Each subject will be assigned a unique 7 digit subject identification number which will be retained throughout the study and that will be unique across all sites. The 7 digit subject identification number (SSSNNNN) will consist of a 3-digit site number (SSS) and a 4-digit subject number (NNNN) at the applicable clinical site. Should a subject be withdrawn from the study, that subject's 7 digit identification number will not be reassigned.

Randomization will be accomplished in blocks of 4 subjects in a 1:1:1:1 ratio with subjects being assigned to treatment with CTAP101 Capsules, IR calcifediol, high-dose cholecalciferol or paricalcitol plus low-dose cholecalciferol. Randomization will occur during Visit 4 provided that each subject is deemed eligible for enrollment based, in part, on laboratory assessments obtained at two preceding visits (Visits 1 and 2). Laboratory assessments obtained at Visit 3 will not be considered in the determination of enrollment eligibility. In the event that the treatment groups become unbalanced for mean baseline body weight as enrollment progresses, the randomization scheme (described immediately above) will be suspended and subjects will be assigned to treatment groups by the following alternative procedure:

Step 1: Calculate the mean body weight for subjects who have been previously entered into the treatment period, in aggregate and by treatment group.

Step 2: Compare the subject's body weight (measured at Visit 1) with the current mean body weight of all subjects who have previously been entered into the treatment period. If the subject's weight is equal to or higher than the current mean body weight of all previously treated subjects, then assign the subject to a treatment group (which still has less than 20 subjects) having the lowest mean body weight. If the subject's weight is lower than the current mean body weight of all previously treated subjects, then assign the subject to a treatment group (which still has less than 20 subjects) having the highest mean body weight.

Step 3 (if needed): If a subject cannot be assigned to a treatment group according to Step 2 (above) and there are fewer than 80 subjects assigned to treatment, then assign the subject to a treatment group (which still has less than 20 subjects) with the most similar mean body weight.

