5.2 Pharmacokinetic properties

The pharmacokinetics of Vitamin D3 is well known.

Absorption

Vitamin D3 is well absorbed from the gastro-intestinal tract in the presence of bile, so the administration with the major meal of the day might therefore facilitate the absorption of Vitamin D3.

Distribution and biotransformation

It is hydroxylated in the liver to form 25-hydroxy-cholecalciferol and then undergoes further hydroxylation in the kidney to form the active metabolite 1, 25-dihydroxy- cholecalciferol (calcitriol).

Elimination

The metabolites circulate in the blood bound to a specific α – globin, Vitamin D3 and its metabolites are excreted mainly in the bile and faeces.

Characteristics in Specific Groups of Subjects or Patients

A 57% lower metabolic clearance rate is reported in subjects with renal impairment as compared with that of healthy volunteers.

Decreased absorption and increased elimination of Vitamin D3 occurs in subjects with malabsorption.

Obese subjects are less able to maintain Vitamin D3 levels with sun exposure, and are likely to require larger oral doses of Vitamin D3 to replace deficits.

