### 3 STUDY DESIGN

#### 3.1 Number of Subjects

Approximately 160 subjects will be screened to enroll approximately 80 eligible subjects with approximately 20 subjects per treatment arm. After signing the informed consent form, prior to any study-related activities, each subject will be assigned a unique 7-digit subject identification number (SSSNNNN) which will be retained throughout the study and that will be unique across all sites. The number will consist of a 3-digit site number (SSS), followed by a 4-digit subject number (NNNN) at the applicable clinical site. Should a subject be withdrawn from the study, that subject's number will not be reassigned.

Randomization will be accomplished in blocks of 4 subjects in a 1:1:1:1 ratio, with subjects assigned to treatment with either CTAP101 Capsules, IR calcifediol, high-dose cholecalciferol, or paricalcitol plus low-dose cholecalciferol. Randomization will occur on Day 1 (Visit 4) provided that each subject is deemed eligible for enrollment based, in part, on laboratory assessments obtained at screening (Days -42 to -36, Visit 1). Laboratory assessments obtained at Days -7 to -1 (Visits 2-3) will not be considered in the determination of enrollment eligibility.

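### The exploratory between-arm PK model in SAP 7.3 leaves out body weight, although the protocol aims to balance the arms on it; precision is lost if weight predicts exposure, and intervals become conservative only if the weight rule is also used.

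*SAP*

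**What the plan says.** The Protocol Synopsis and Section 3.1 describe about 80 subjects "randomized 1:1:1:1 (approximately 20 per arm, balanced for body weight". The working method in Protocol 5.4 is permuted blocks with no weight stratum: "Randomization will be accomplished in blocks of 4 subjects in a 1:1:1:1 ratio with subjects being assigned to treatment" with one of the four regimens. A second method replaces it under a condition: "In the event that a significant difference in mean baseline body weight among subjects by treatment group emerges as enrollment progresses". Protocol 9.3 words the condition differently: "In the event that the treatment groups become unbalanced for mean baseline body weight as enrollment progresses". Neither section gives a test, a threshold or a time of checking.

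Once triggered, the rule is deterministic. For a subject at or above the running mean weight the instruction is to "assign the subject to a treatment group (which still has less than 20 subjects) having the lowest mean body weight"; a lighter subject goes to the open arm with the highest mean. The weight used is the one from Visit 1, which Protocol 6.3 (Table 1) collects in every subject.

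SAP 3.1 describes only the blocks ("Randomization will be accomplished in blocks of 4 subjects in a 1:1:1:1 ratio, with subjects assigned to treatment"), and the visible SAP does not mention the weight rule. For the PK comparison SAP 7.3 states: "The model will include a term for treatment and BL calcifediol as a covariate". The PROC MIXED code agrees with the text. The output is least-squares differences with 95% confidence intervals and P values, and the analysis is labelled exploratory.

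**The concern.** A variable that is important enough to balance on, and possibly to assign treatment by, would normally appear in the model that compares the arms. The protocol's appendices suggest that it could matter for exposure. The high-dose cholecalciferol product information says that obese subjects "are likely to require larger oral doses of Vitamin D3 to replace deficits", the immediate-release calcifediol information lists obesity among the factors in choosing a dose, and no dose in the trial is scaled to weight.

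Two things could follow from leaving weight out. First, variation that weight could explain stays in the residual, which costs precision with only about 20 subjects per arm. Second, if the weight rule is used, the design removes weight differences between arms while the model still counts weight variation as error, so its standard errors overstate the true variability of the treatment difference.

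**Working it through.** The plan has no figure to reproduce: SAP 3.2 gives about 80 subjects on practical grounds, with no SD, effect size or power. What can be checked is how the SAP 7.3 interval behaves.

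**Inputs from the documents.** 80 subjects, 4 arms, 20 per arm; the model terms in SAP 7.3; blocks of 4 and Steps 1 to 3 of Protocol 5.4.

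**Assumptions.** The share of PK variance that weight explains given baseline calcifediol (R², the square of the partial correlation ρ); a common weight slope and equal variances in all arms; and when the weight rule starts.

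**1. Width.** The SAP model has 4 + 1 = 5 mean parameters, so 80 − 5 = 75 residual degrees of freedom; with weight, 74. The ratio of interval widths, with weight to without, is about √[(1 − R²) × 75/74]:

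| Assumed R² | Ratio | Change on adding weight |
|---|---|---|
| 0 | √(1.0135) = 1.007 | 0.7% wider |
| 0.10 | √(0.9122) = 0.955 | about 5% narrower |
| 0.20 | √(0.8108) = 0.900 | 10% narrower |
| 0.30 | √(0.7095) = 0.842 | about 16% narrower |

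Break-even is where (1 − R²) × 75/74 = 1, so R² = 1/75 = 0.0133 and ρ = 0.115, or about 0.12. Simulation (6,000 trials per setting, blocks only) agrees with the formula: 1.007 at ρ = 0, 0.961 at 0.3 (formula 0.960) and 0.872 at 0.5 (formula 0.872).

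**2. Coverage of the SAP interval, by allocation.** These are simulations of one pairwise 95% interval with a true difference of zero.

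- Blocks of 4 only: 94.7 to 95.1% for every ρ from 0 to 0.7. The interval is correctly sized.
- Weight rule started when a one-way ANOVA on weight gives p < 0.05, checked before each assignment from subject 9 (an assumed trigger): it fired in 31% of trials. Overall coverage was 95.7, 96.1 and 97.0% at ρ = 0.3, 0.5 and 0.7. With p < 0.10 it fired in 48%, and coverage was 95.7, 96.6 and 97.9%.
- Weight rule from subject 21, R² = 0.10, 0.20, 0.30: the model's standard error is 0.318 to 0.320 SD units. The true SD of the estimate is 0.301 to 0.306, 0.286 to 0.295 and 0.272 to 0.275 over separate sets of runs. The standard error is therefore too large by about 4 to 6% (0.318/0.306 to 0.318/0.301), 8 to 11% (0.318/0.295 to 0.318/0.286) and 16 to 17% (0.319/0.275 to 0.319/0.272). Coverage is about 96 to 98%.
- At ρ = 0, coverage is nominal (94.9 to 95.2%) for blocks only, for both triggers, and with the rule running from subject 9.

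With weight in the model and equal variances, coverage is about 95% under each of these allocations.

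**3. Sensitivity to the assumptions**, for CTAP101 against immediate-release calcifediol, with the rule never used or running from subject 21.

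- Weight acting only in the cholecalciferol arm: adding weight multiplies the width by 0.991 to 1.003, and coverage without it is 94.4 to 95.0%. There is essentially nothing to gain.
- Residual SDs unequal by arm (assumed 1:2:1:0.3 or 1:3:1:0.3, in the order CTAP101, immediate-release calcifediol, cholecalciferol, paricalcitol): the SAP interval covers 84 to 93%, which is too narrow, and adding weight leaves 85 to 89%.

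**The case against.** The strongest case against acting has four parts.

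*The weight rule is a contingency.* A reader might infer that the SAP intervals are too wide for the trial's allocation method. The documents do not support that. The default is blocks of 4 without a weight stratum, and under it the intervals have nominal coverage. This part of the objection stands in full.

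*The strength of the weight effect is unknown.* No section gives a correlation between weight and any PK parameter. The product statement quoted above concerns vitamin D3. The immediate-release calcifediol information says that calcifediol is stored in fat less than vitamin D is. The paricalcitol arm receives only 800 IU of cholecalciferol a day. Baseline calcifediol, already in the model, may carry part of any weight effect. All of this stands and limits confidence in the size of the gain. It does not remove the case for the term, because the cost if weight is irrelevant is 0.7% of width.

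*Adding weight does not guarantee correct coverage.* A reader might also infer that the SAP's standard errors and P values are simply too large and that weight puts them right. With unequal variances between arms they can be too small, and weight does not repair that. This stands, but it is a separate issue.

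*The analysis is exploratory*, in a descriptive study with no efficacy endpoints, and SAP 7.3 allows other analyses if the model proves unsuitable. This lowers the severity. However, that clause does not name weight, and SAP Section 4 would class a weight-adjusted analysis devised after database lock as post hoc.

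**Conclusion.** The omission is certain from the SAP 7.3 text and code, and it sits badly with the protocol's aim of balancing on weight. The consequences are conditional. Precision is lost only if the partial correlation of weight with exposure exceeds about 0.12; the narrowing available is then about 5, 10 or 16% for an assumed 10, 20 or 30% of variance, given a common slope and equal variances. Conservative intervals need two things together: the weight rule in use and weight being prognostic.

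The point concerns efficiency and, at most, mild over-coverage. It does not show bias or excess false positives from leaving weight out. It is limited to SAP 7.3: Protocol 9.8 also mentions an optional ANOVA with no weight term stated, and the redacted part of the SAP cannot be judged. Severity is low to moderate. Confidence is high for the omission and low for the size of the gain.

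**What to change.** Before database lock, add Visit 1 body weight as a continuous covariate in the SAP 7.3 text and in the code, MODEL aval = trtp base_calcifediol base_weight, and make this the analysis reported in Table 14.2.1.3. The ESTIMATE statements need no change, since they use only the treatment coefficients. The cost is one sentence, one model term and one of 75 residual degrees of freedom. No new data are needed, because weight is already collected at Visit 1. The change does not deal with unequal residual variances between arms, which need separate attention.

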3 INVESTIGATIONAL PLAN

3.1 Overall Study Design and Plan

This is a phase 4, multi-center, open-label study to evaluate the comparative safety, efficacy, and PK and **CCI** profiles of CTAP101 Capsules, IR calcifediol, high-dose cholecalciferol, and paricalcitol plus low-dose cholecalciferol to treat SHPT in male and female subjects aged at least 18 years with stage 3 or 4 CKD and VDI. The study will be conducted at multiple sites within the US. Approximately 160 subjects will be screened to enroll approximately 80 eligible subjects who will be randomized 1:1:1:1 (approximately 20 per arm, balanced for body weight) to receive the following medications:

Test Products, Dose, and Mode of Administration:

CTAP101 Capsules (30 mcg/capsule), 60 mcg, by the oral route

[figure not shown]
[figure not shown]
[figure not shown]
[figure not shown]
[figure not shown]
[figure not shown]
Calcifediol immediate-release (IR) (266 mcg/capsule), 266 mcg, by the oral route

Cholecalciferol (50,000 IU/capsule), 300,000 IU, by the oral route

Paricalcitol (1 mcg/capsule) plus cholecalciferol (800 IU/capsule), 1 or 2 mcg plus 800 IU, by the oral route.

If a significant difference in average weight among subjects by treatment group emerges during the course of the study, subjects may be placed into specific treatment groups rather than randomly assigned, in order to try and achieve more balance in the treatment groups by body weight.

The subjects will be housed in a phase 1 unit for approximately 14 to 26 hours at the beginning of the study and on study Day 29 to provide the blood samples required for a detailed determination of the PK profiles for serum calcifediol and **CCI**

Blood samples for some of the PK/**CCI** assessments will be collected in the phase 1 unit at -2, 0, 2, 4, 6, and 12 hours either in the phase 1 unit or during outpatient visit, at 24 hours; during outpatient visit for 48 hours; and then weekly following the first dose and the Day 29 dose of each medication. Blood samples for other **CCI** assessments will be collected at less frequent intervals. Urine collections (24-hour) will be obtained at pre-treatment baseline (Visits 2 and 3), starting immediately after dosing on Day 1 (Visit 4) and Day 29 (Visit 10) and at the end of study (Visit 16) or early termination (ET). The schedule for blood and urine sample collections is delineated in [Section 7](#) (Study Activities) and in [APPENDIX 1](#).

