4.4 Special warnings and precautions for use

- The serum levels of 25-OH-cholecalciferol reflect the patient's vitamin D status, but in order to obtain an adequate clinical response to the oral administration of calcifediol, there must also be adequate calcium intake in the diet. Therefore, to control the therapeutic effects, in addition to the 25-OH-cholecalciferol, the calcium, phosphorous, alkaline phosphatase, and urinary calcium and phosphorous in the serum must be monitored over 24 hours; a drop in the

serum levels of alkaline phosphatase normally precedes the appearance of hypercalcaemia. Once these parameters are normal in the patient and the patient is on a maintenance treatment regimen, the above-mentioned measurements must be taken, in particular the serum levels of 25-OH-calciferol and calcium.

- **Hepatic or gallbladder insufficiency:** In the event of hepatic insufficiency, an inability to absorb calcifediol may occur through bile salts not being produced.
- **Renal insufficiency:** Administration with caution is advised. The use of this medicinal product in patients with chronic kidney disease must be accompanied by regular checks of plasma calcium and phosphorous, and to prevent hypercalcaemia. As the kidneys will give rise to calcitriol, in the event of severe renal insufficiency (renal creatinine clearance less than 30 mL/minute) a very significant decrease in the pharmacological effects may occur.
- **Cardiac insufficiency:** Particular caution is required. The individual's calcium level must be monitored at all times, particularly in patients undergoing treatment with digitalis medication, as it may cause hypercalcaemia and the appearance of arrhythmia; it is advised to perform these measurements twice a week at the start of treatment.
- **Hypoparathyroidism:** 1-alpha-hydroxylase shall be activated by the **CCI** [REDACTED], therefore in the event of parathyroid insufficiency, the calcifediol activity may decrease.
- **Renal calculi:** The calcium level must be controlled as vitamin D, by increasing calcium absorption, may aggravate the symptoms. Vitamin D levels must only be administered in these patients if the benefits outweigh the risks.
- In patients with long-term immobilisation, dose reduction may be necessary on occasion to avoid hypercalcaemia.
- There are diseases that affect the intestine's capacity to absorb vitamin D, as in the case of malabsorption syndrome or Crohn's disease.

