### **6.3 Demographics and Baseline Characteristics**

Descriptive statistics (ie, number of subjects, mean, SD, median, minimum, and maximum) will be calculated for continuous demographic and BL characteristic variables (age at Screening, weight at BL, height at Screening, and body mass index [BMI] at BL) and counts and percentages will be tabulated for categorical demographic variables (sex, race, and ethnicity) for each analysis population by treatment and overall.

A data listing will be provided for all demographic data. In addition, the BL characteristics of weight, height, and BMI will be included in the vital sign data listing.

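### The exploratory between-arm calcifediol PK model and the baseline tables leave out kidney function, although eGFR is collected, defines entry and is described as relevant to vitamin D metabolism

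*SAP*

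**What the plan says.** SAP 7.3 plans an exploratory comparison of calcifediol PK parameters in the PK population, with least-squares differences, 95% intervals and P values. On covariates it says "The model will include a term for treatment and BL calcifediol as a covariate", and the code agrees: "MODEL aval = trtp base_calcifediol". SAP 6.3 limits the continuous baseline variables to "age at Screening, weight at BL, height at Screening, and body mass index [BMI] at BL", with sex, race and ethnicity as the categorical ones. Protocol 9.5 adds tobacco, nicotine and alcohol history. Neither list has eGFR or CKD stage.

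Kidney function appears elsewhere:
- Entry requires eGFR of 15 to <60 mL/min/1.73m2 (Protocol 4.2), measured at Visit 1 (Protocol 7.1.1 and Appendix 1).
- CKD stage is recorded under medical history, which is listed and summarized by system organ class and preferred term (SAP 6.4).
- Creatinine and blood urea nitrogen are in the full chemistry panel (Protocol Table 2), drawn at Visits 1, 2, 3, 10 and 16. Chemistry is summarized by arm with change and shifts from baseline in the Safety population (SAP 9.2, Tables 14.3.5.7 and 14.3.5.8).
- Remaining laboratory parameters go to listings (SAP 9.9).

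On allocation, SAP 3.1 says "Randomization will be accomplished in blocks of 4 subjects in a 1:1:1:1 ratio" and Protocol 3.1 says "approximately 20 per arm, balanced for body weight". If mean weights drift apart, "the randomization scheme (described immediately above) will be suspended" and a weight rule assigns subjects (Protocol 5.4).

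On relevance, Protocol 1.3 says low 25-hydroxyvitamin D becomes more common as kidney disease advances. Protocol 1.4 names excess CYP24A1, the catabolic enzyme, and urinary loss of binding protein as causes. Appendix 3, section 5.2, adds for cholecalciferol: "A 57% lower metabolic clearance rate is reported in subjects with renal impairment as compared with that of healthy volunteers". Appendix 4, section 4.4, says cholecalciferol metabolism is abnormal in severe renal insufficiency. Appendix 2, section 4.4, says of IR calcifediol: "in the event of severe renal insufficiency (renal creatinine clearance less than 30 mL/minute) a very significant decrease in the pharmacological effects may occur".

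**The concern.** The trial enrols a fourfold range of eGFR (15 to <60) with about 20 subjects per arm, and its own documents treat kidney function as relevant to how vitamin D is handled. The value is already collected on everyone before the first dose. Leaving it out of the model forgoes precision in a study with no power calculation. Leaving it out of the baseline tables means a reader of the PK comparison cannot see whether the modelled arms were alike in the characteristic that defines the population.

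**Working it through.** The plan has no power calculation to reproduce. Its 4 x 20 = 80 is consistent.

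**1. How often the arms would differ by chance (20 per arm, simple randomization).** The standard error of a difference in mean eGFR, in SD units, is sqrt(2/20) = 0.316. Results for one pair are normal tails; those for the three CTAP101 contrasts come from 400,000 simulated trials.
- Difference above 0.25 SD: 43% for one contrast, 77% for at least one of the three.
- Difference above 0.5 SD: 11% and 26%. With an assumed eGFR SD of 10-13, 0.5 SD is 5-6.5 mL/min/1.73m2.
- Stage 4 share differing by at least 20 percentage points (overall share assumed 20-50%): 16-27% and 36-55%.
- Differing by at least 30 points: 3-8% and 7-20%.

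A moderate difference in at least one contrast is common. A large one in any given contrast is not.

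**2. Which parameters could respond to clearance.** Take mono-exponential decline with half-life 18 or 21 days (Appendix 2, section 5.2) or 30 days (Protocol 3.2), with k = ln(2)/half-life. Average exposure over T days after one dose is (1 - exp(-kT))/(kT). Cut k by 57% as a deliberately large test:
- T = 1 day: 0.981 becomes 0.992 at 18 days, and 0.989 becomes 0.995 at 30 days. The ratios are 1.011 and 1.007, a change of about 1%.
- T = 28 days: 0.612 becomes 0.800, and 0.736 becomes 0.873. The ratios are 1.31 and 1.19.
- Daily dosing, Day 29 level, using the sum of exp(-kj) for j = 0 to 28: ratios 1.30 and 1.18.

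So 24-hour exposure after the first dose hardly depends on clearance, while Day 29 and 28-day exposure could move by 18-31% in this test.

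**3. From imbalance to shift in the comparison.** If stage 4 subjects have r times the exposure of stage 3 subjects, a 20-point imbalance multiplies the ratio of geometric means by r^0.2. For an assumed r of 1.1 to 1.5 this is 1.019 to 1.084, or 2-8%. Putting the whole 57% between the stages (r = 1/0.43 = 2.33) gives 1.18, but the documents do not support that value. The SAP models the untransformed parameter, so these ratios are only a gauge.

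**4. What adjustment gains.** The present model uses 5 parameters (intercept, three treatment terms, baseline calcifediol), leaving 80 - 5 = 75 residual degrees of freedom; adding eGFR leaves 74. The standard error is multiplied by sqrt((1 - R2) x 75/74), where R2 is the share of residual variance that eGFR explains:
- R2 = 0.05: sqrt(0.95 x 1.0135) = 0.981.
- R2 = 0.10: 0.955.
- R2 = 0.15: sqrt(0.85 x 1.0135) = 0.928.

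Without the degree-of-freedom correction the ends are sqrt(0.95) = 0.975 and sqrt(0.85) = 0.922. Standard errors therefore fall by about 2-8%. Before that correction, this equals 80/0.95 = 84 to 80/0.85 = 94 subjects under the present model.

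**The case against.** The case against is substantial.

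- **Visibility.** A reader might infer that an imbalance would go unseen. It would not: baseline creatinine and blood urea nitrogen are tabulated by arm, and medical history is summarized by arm, though it is unclear whether its preferred terms separate CKD stages. This stands. What remains missing is eGFR and stage by arm, above all for the PK population.
- **Bias.** A reader might infer that chance imbalance makes the contrasts biased. Under intact randomization it does not, because the interval already allows for it. This stands, with two limits. The weight rule ignores kidney function, and the PK population is selected after randomization for no major deviations and sufficient data (SAP 5.4), so neither guarantees random balance.
- **Size of the renal effect.** A reader might take the 57% as the effect at issue. It concerns vitamin D3 against healthy volunteers, whereas all subjects here have CKD and the analyte is calcifediol. The IR calcifediol warning concerns pharmacological effect, which the label ties to calcitriol formation in the kidney, and not exposure. No passage quantifies calcifediol exposure across eGFR 15 to <60. These passages show relevance only.
- **Proportion.** The main regimen contrast may dwarf a 2-8% shift: 28 x 60 = 1,680 mcg against 266 mcg, which at about 25% bioavailability (Protocol 1.9, fasting) and 75-80% absorption (Appendix 2) is 420 against 200-213 mcg, about twofold. Baseline calcifediol may also stand in partly for kidney function. Both points limit the gain without removing it.
- **Exploratory status.** SAP 7.3 permits alternative analyses, but only for insufficient data or model problems. That does not prespecify a renal adjustment.

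**Conclusion.** The point holds as a low-cost improvement, and it is firmest for the missing table rows. The SAP 7.3 model and the baseline tables omit a relevant baseline value that is already collected. The gain is mainly precision: about 2-8% in standard errors if R2 is 5-15%, a range that is assumed. It also offers some protection if the weight rule is used or if PK exclusions differ by arm. It applies mainly to Day 29 Cmax, AUC and Cavg and to 28-day parameters; first-dose 24-hour parameters are nearly insensitive.

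The imbalance probabilities rest on assumed stage shares and an assumed eGFR SD, and the exposure figures on a simple decline model. A reader might also infer that allocation should have been stratified by kidney function. The material does not require that: an unstratified design is a fair trade-off at this size. SAP section 8 is redacted, so the pharmacodynamic models are not judged.

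**What to change.** - In SAP 7.3, prespecify Visit 1 eGFR as a continuous covariate for Day 29 and 28-day parameters by appending `base_eGFR` to the MODEL statement after baseline calcifediol. SAP 7.2 reads the monthly arms' first-dose Cmax over 28 days, so assign parameters by time window and not by the Day 1 label. Leave first-dose 24-hour parameters as they are.
- State which eGFR value counts if a subject was retested after Visit 1 (Protocol 7.1.1).
- Add eGFR (continuous) and CKD stage (3 or 4) by arm to Tables 14.1.2-14.1.5. Table 14.1.5 covers the PK population and is the one that matters most.
- Leave allocation unchanged.

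Cost: one degree of freedom of about 75 and two table rows, with no new data. The change should be made before database lock so that it counts as prespecified.
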